8.2. Prophylactic Immune Tolerance Induction (ITI) Regimen

To prevent the risks of an inflammatory response and to protect AAV-transduced cells from immune response to the AAVrh8 capsid and/or transgene, participants will be immunosuppressed prior to administration of AXO-AAV-GM2 treatment. The ITI regimen will be maintained as described below.

Starting on Day -7 of the study, the following will be initiated:

- Rituximab* at 375 mg/m² BSA (IV infusion)
 - *Pre-medication for rituximab infusion will include:
 - acetaminophen 10-15 mg/kg given either PO, g-tube or rectal one time prior to infusion (may repeat q 4 hours for temperature >38.3°C)
 - diphenhydramine 1 mg/kg given either PO, g-tube or IV one time prior to infusion (may repeat 1 mg/kg IV PRN)
- Solu-Medrol at 10 mg/kg (IV infusion)
- Sirolimus* at 1.5 mg/m² BSA/day (PO or by feeding tube) *adjustment permitted to achieve trough levels of 7-12 ng/mL
- Prednisolone at 1-2 mg/kg/day (PO or by feeding tube)
- Lansoprazole at 1-1.5 mg/kg/day (PO or by feeding tube)
- Trimethoprim/sulfamethoxazole 2.5 mg/kg/day BID on 2 consecutive days per week (PO or by feeding tube) or per PI discretion

Day -2, Day 1 (BiTh Infusion Day), Day 2 (ICM/IT Infusion Day):

• Rituximab* at 375 mg/m² BSA (IV infusion), as needed for persistent CD20 count ≥ 5%

*Pre-medication for rituximab infusion will include:

- acetaminophen 10-15 mg/kg given either PO, g-tube or rectal one time prior to infusion (may repeat q 4 hours for temperature >38.3°C)
- diphenhydramine 1 mg/kg given either PO, g-tube or IV one time prior to infusion (may repeat 1 mg/kg IV PRN)
- Continuation of sirolimus*, prednisolone, and lansoprazole dosing (PO or by feeding tube)
 - *adjustment permitted to achieve trough levels of 7-12 ng/mL
- Continuation of trimethoprim/sulfamethoxazole 2.5 mg/kg/day BID on 2 consecutive days (PO or by feeding tube) or per PI discretion

Day 2-8:

- Continuation of sirolimus*, prednisolone, and lansoprazole dosing (PO or by feeding tube)
 - *adjustment permitted to achieve trough levels of 7-12 ng/mL
- Continuation of trimethoprim/sulfamethoxazole 2.5 mg/kg/day BID on 2 consecutive days per week (PO or by feeding tube) or per PI discretion

Confidential Page 40 of 97

Clinical Study Protocol: AXO-GM2-001

Version 8.0, 09 June 2023

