• IV immunoglobulin (IVIG) ~1000 mg/kg administration – initiate only if immunoglobulin levels fall below 500 mL/dL. Dose will be adjusted to maintain serum trough levels of 500-1000 mg/dL. Will occur after vector infusion.

Day 15, Day 22:

- Continuation of sirolimus*, prednisolone, and lansoprazole dosing (PO or by feeding tube)
 - *adjustment permitted to achieve trough levels of 7-12 ng/mL
- Continuation of trimethoprim/sulfamethoxazole 2.5 mg/kg/day BID on 2 consecutive days per week (PO or by feeding tube) or per PI discretion

Week 4/Month 1:

- Continuation of sirolimus*, prednisolone, and lansoprazole dosing (PO or by feeding tube)
 - *adjustment permitted to achieve trough levels of 7-12 ng/mL
- Continuation of trimethoprim/sulfamethoxazole 2.5 mg/kg/day BID on 2 consecutive days per week (PO or by feeding tube) or PI discretion
- IVIG ~1000 mg/kg if IgG levels are below 500 mL/dL. Dose will be adjusted to maintain serum trough levels of 500-1000 mg/dL.

Week 6, Week 8, Week 10:

- Continuation of sirolimus*, prednisolone, and lansoprazole dosing *adjustment permitted to achieve trough levels of 7-12 ng/mL
- Continuation of trimethoprim/sulfamethoxazole
- IVIG \sim 1000 mg/kg if IgG levels are below 500 mL/dL. Dose will be adjusted to maintain serum trough levels of 500-1000 mg/dL.

Week 12/Month 3 to Week 20/Month 5:

- Initiate prednisolone tapering regimen:
 - Week 12-13: Reduce Dose by 50%
 - Week 13-14: Reduce week 12-13 Dose by 50%
 - Week 14-15: Reduce week 13-14 Dose by 50%
 - Week 15-16: Reduce week 14-15 Dose by 50% then stop
- Lansoprazole to be discontinued following completion of prednisolone tapering
- Continuation of sirolimus*
 - *adjustment permitted to achieve trough levels of 7-12 ng/mL
- Continuation of trimethoprim/sulfamethoxazole
- IVIG \sim 1000 mg/kg if IgG levels are below 500 mL/dL. Dose will be adjusted to maintain serum trough levels of 500-1000 mg/dL.

Week 24/Month 6

• Initiate weaning of sirolimus:

Confidential Page 41 of 97

Clinical Study Protocol: AXO-GM2-001

Version 8.0, 09 June 2023

- Week 24-25: reduce dose by 50% (PO or by feeding tube)
- Week 25-26: reduce Week 24-25 dose by 50% (PO or by feeding tube)
- Week 26-27: reduce Week 25-26 dose by 50% (PO or by feeding tube) then stop
- Trimethoprim/sulfamethoxazole to be discontinued following completion of sirolimus wean

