- 15. Sirolimus oral at 1.5 mg/m² BSA; Adjust dose to achieve serum trough levels of 7-12 ng/mL as needed. To be weaned starting Visit 12/Week 24 according to the following regimen: Week 24-25: reduce dose by 50%; Week 25-26: reduce Week 24-25 dose by 50%; Week 26-27: reduce Week 25-26 dose by 50% then stop
- 16. Prednisolone 1-2 mg/kg/day, to be tapered starting Visit 9/Week 12 according to the following regimen: Week 12-13: reduce dose by 50%; Week 13-14: reduce week 12-13 dose by 50%; Week 14-15: reduce week 13-14 dose by 50%; Week 13-14 dose by 50% then stop.
- 17. The dose of trimethoprim/sulfamethoxazole should be 2.5 mg/kg/day BID on 2 consecutive days per week (PO or by feeding tube) or per PI discretion, to be discontinued following completion of sirolimus wean.
- 18. Lansoprazole suspension of 1 to 1.5 mg/kg/day PO, to be discontinued following completion of prednisolone tapering.
- 19. IVIG administration 1 gm/kg (1000 mg/kg) if IgG levels < 500 mL/dL. Dose adjusted to maintain serum trough levels of 500-1000 mg/dL after vector infusion. On Day 1, IVIG administration will occur later in the day, after treatment infusion has completed.
- 20. Divided between clinical and research analyses. Visit 1b (Day -2) CSF collection should be pre-administration.
- 21. Anti-seizure drug levels will be assessed as needed after Day -2
- 22. Appropriate neuro-cognitive assessments will be determined for each participant. We expect all participants will be assessed via the Vineland 3. Available additional juvenile assessments include the Wechsler, WPPSI, BSID-III depending on the participant's age and capabilities.
- 23. CGI-S will be administered at Visit A. CGI-I will be administered at Visits 5, 9, 12, 13, 14, and 15. All neuro-cognitive assessments with the exception of the Vineland 3 should be videotaped.
- 24. Juvenile motor assessments and motor classifications include the GMFM-88, GMFC-MLD, 9 Hole Peg Test, Timed Motor Function Tests (10 Meter Walk/Run, Time to Rise From Floor, Time Up 4 Stairs), MACs. All motor assessments with the exception of the MACs should be videotaped.

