- 9. Blood will be collected for research as tolerated by the participant and will be frozen for later use or used for the isolation of serum or PBMCs. The amount of research blood collected, and its intended use, will vary between visits based on the overall volume of blood collected within a 1-week period remaining < 10 mL. Sample prioritization will be determined by investigator and Sponsor if collected blood volume is limited. Collect blood on Visit B (Day -16) prior to immunosuppression.. Blood collected for research can include anti-AAVrh8 antibodies (ADA), transgene antibodies (ADA) and neutralizing antibodies (Nabs) if needed. The priority should be the antibodies followed by the serum HEXA activity and then GM2 ganglioside levels in serum.
- 10. Infectious disease testing will be performed as clinically indicated (i.e., based on Medical History) and will include HIV, hepatitis A, B and C, herpes simplex virus, cytomegalovirus, Epstein Barr virus, varicella zoster virus, and toxoplasmosis
- 11. Measurements include systolic and diastolic blood pressure, pulse rate per minute, respiratory rate per minute, and temperature
- 12. Comprehensive exam or limited exam at the discretion of the clinician based on participant's status. Exams may be videotaped. For Visit 1b (Day 2), perform neurologic checks every 2h for the first 24h, and full physical and neurological exam 24h, 48h, and 72h post infusion while inpatient.
- 13. Caregivers will have option to have central venous catheter inserted into participants prior to surgical gene transfer to ensure venous access and reduce difficulty and pain associate with blood draws during the study
- 14. Rituximab IV infusion at 375 mg/m² body surface area (BSA). As needed at Day -2 for persistent CD20 count greater than or equal to 5%
- 15. Solu-Medrol IV infusion at 10 mg/kg
- 16. Sirolimus oral at 1.5 mg/m² BSA; Adjust dose to achieve serum trough levels of 7-12 ng/mL as needed. To be weaned starting Visit 12/Week 24 according to the following regimen: Week 24-25: reduce dose by 50%; Week 25-26: reduce Week 24-25 dose by 50%; Week 26-27: reduce Week 25-26 dose by 50% then stop
- 17. Prednisolone 1-2 mg/kg/day, to be tapered starting Visit 9/Week 12 according to the following regimen: Week 12-13: reduce dose by 50%; Week 13-14: reduce week 12-13 dose by 50%; Week 14-15: reduce week 13-14 dose by 50%; Week 15-16: reduce week 13-14 dose by 50% then stop.

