- 18. The dose of trimethoprim/sulfamethoxazole 2.5 mg/kg/day BID on 2 consecutive days per week (PO or by feeding tube) or per PI discretion, to be discontinued following completion of sirolimus wean.
- 19. Lansoprazole suspension of 1 to 1.5 mg/kg/day PO, to be discontinued following completion of prednisolone tapering.
- 20. IVIG administration 1 gm/kg (1000 mg/kg) if IgG levels < 500 mL/dL. Dose adjusted to maintain serum trough levels of 500-1000 mg/dL after vector infusion. On Day 1, IVIG administration will occur later in the day, after treatment infusion has completed.
- 21. Divided between clinical and research analyses. Visit 1b (Day -2) CSF collection should be pre-administration.
- 22. Participants must have a swallow evaluation test performed within 6 months prior to AXO-AAV-GM2 administration to assess risk of aspiration. If aspiration risk is identified, it must be clinically managed prior to surgical procedures. Participants must have a swallow evaluation test performed at baseline and a clinical assessment of swallowing and a swallow study, if warranted, at Visit 9 (Week 12), Visit 12 (Week 24), Visit 13 (Week 48), and yearly thereafter for Years 2-5 (see Table 17).
- 23. May be completed if visit occurs in person however not if the visit is completed as a tele-health
- 24. Tele-health will occur if Pt does not come to site in person

AN - As Needed

Confidential Page 62 of 97

Clinical Study Protocol: AXO-GM2-001

Version 8.0, 09 June 2023

 Table 16:
 Schedule of Juvenile-Onset Participant LTFU

Schedule of Activities	Visit 16	Visit 17	Visit 18	Visit 19	Visit 20
	Week 120	Week 144	Week 168	Week 192	Week 240
	±28d	±28d	±28d	±28d	±28d
Vital Signs	X^1	X^1	X ¹	X^1	X^1
Weight	X ¹	X ¹	X ¹	X^1	X^1
Height	X^1	X^1	X ¹	X^1	X^1
Physical Examination	X ¹	X ¹	X ¹	X^1	X^1
Neurologic Examination (may be videotaped)	X ¹	X ¹	X ¹	X^1	X^1
Tele-health follow-up	X^2	X^2	X^2	X^2	X^2
Participant Appropriate Neuro-Cognitive Assessments		X ¹		X^1	X^1
Clinical Global Impression		X ¹		X^1	X^1
Motor Assessments		X ¹		X^1	X^1
BAER/VER/SSEP		X^1			
MRI, MRS, DTI		X^1		X^1	X^1
CBC with auto-differential	X^1	X ¹	X ¹	X^1	X^1
Comprehensive metabolic profile	X ¹	X ¹	X ¹	X^1	X^1
CH50 – AN due to platelet count decrease	AN	AN	AN	AN	AN
CSF HexA activity level, GM2 ganglioside		X ¹		X^1	X^1
CD 19, 20 count	AN	AN	AN	AN	AN
IgG levels	AN	AN	AN	AN	AN
Research blood collection	X ¹				
Anti-AAVrh8 antibodies (ADA)	X^1	X^1	X ¹	X^1	X^1
Transgene antibodies (ADA)	X ¹				

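### Section 8.2 and the Table 14/15 schedules give different immunosuppression instructions on repeat rituximab days, the last prednisolone step and the IVIG day

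*Combined protocol and SAP*

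**What the plan says.** **Rituximab.** After the Day -7 infusion, Section 8.2 places a repeat infusion under the heading "Day -2, Day 1 (BiTh Infusion Day), Day 2 (ICM/IT Infusion Day", to be given "as needed for persistent CD20 count ≥ 5" per cent. Table 14 footnote 13 (juvenile) and Table 15 footnote 14 (infantile) both read "As needed at Day -2 for persistent CD20 count greater than or equal to 5" per cent. Both grids show rituximab as planned at Visit C (Day -7) and as needed at Visit D (Day -2), with nothing at Visit 1a or 1b.

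**Prednisolone.** The starting dose is given as "Prednisolone at 1-2 mg/kg/day (PO or by feeding tube"). From Week 12 it is tapered in weekly steps. For the last step Section 8.2 says "Week 15-16: Reduce week 14-15 Dose by 50% then stop", and Table 15 footnote 17 says "Week 15-16: reduce week 13-14 dose by 50% then stop". Table 14 footnote 16, in the text as read, runs "Week 14-15: reduce week 13-14 dose by 50%; Week 13-14 dose by 50% then stop". It has no label for the last week and also refers back to Week 13-14.

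**IVIG.** Section 8.2 lists the first IVIG under Day 2-8, only if immunoglobulin is low, and places it after vector infusion. The grids of both tables mark it as needed at Visit 1b (Day 2) and leave Visit 1a (Day 1) blank. Table 14 footnote 19 and Table 15 footnote 20 say "On Day 1, IVIG administration will occur later in the day, after treatment infusion has completed".

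**IgG unit.** Section 8.2 and both IVIG footnotes write the trigger as 500 mL/dL and the trough target as 500-1000 mg/dL.

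**The concern.** These are operative treatment instructions, and all of them stand in the current text. A team working from the schedule and a team working from Section 8.2 could each follow the protocol and give different treatment. The same act could then be counted as compliant or as a deviation, depending on the page consulted. Section 8.2.1 also sends children who have had rescue steroids back to the scheduled wean, and the schedule and Section 8.2 write that wean differently for infantile participants. Section 8.1.2 places all Stage 2 participants, who are infantile-onset, under Table 15, where the prednisolone conflict is firmest. Immunosuppression response markers are among the Stage 1 secondary endpoints, so a single clear description of the regimen is needed to interpret them.

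**Working it through.** The plan states no figure for these differences, so there is none to reproduce. The check compares the texts and runs both written tapers.

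**1. Rituximab.** As-needed days after Day -7:
- Section 8.2: Day -2, Day 1, Day 2, which is 3 permitted days.
- Table 14 and 15 footnotes and grids: Day -2, which is 1 permitted day.

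These are counts of permission, not of doses given. The trigger is a CD20 count. Both grids schedule a CD19/20 count at Visits B, C and D, none on Day 1, and one as needed on Day 2. The schedule therefore does not fully support the extra Section 8.2 days. A Day -2 result might inform a Day 1 decision, but neither text says so.

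**2. Prednisolone.** Inputs: starting dose D = 1-2 mg/kg/day (Section 8.2), steps of 50%, 7 days per step.

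| Week | Section 8.2 | Table 15 footnote 17 |
|---|---|---|
| 12-13 | 0.5 D | 0.5 D |
| 13-14 | 0.5 × 0.5 D = 0.25 D | 0.25 D |
| 14-15 | 0.5 × 0.25 D = 0.125 D | 0.125 D |
| 15-16 | 0.5 × 0.125 D = 0.0625 D | 0.5 × 0.25 D = 0.125 D |

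- Last week: 6.25% against 12.5% of D, a factor of 2. In dose terms this is 0.0625-0.125 against 0.125-0.25 mg/kg/day. The footnote's last step equals the week before, so it is not a reduction.
- Four-week total, Section 8.2: 7 × (0.5 + 0.25 + 0.125 + 0.0625) D = 6.5625 D.
- Four-week total, footnote 17: 7 × (0.5 + 0.25 + 0.125 + 0.125) D = 7.0 D.
- Difference: 0.4375 D, or 0.44-0.88 mg/kg; 7.0 / 6.5625 - 1 = 6.7%.

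**3. IVIG.** First possible day is Day 2 in Section 8.2 and in both grids, and Day 1 in footnotes 19 and 20. The footnotes therefore disagree with their own tables as well as with Section 8.2.

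**4. IgG unit.** mL/dL is a ratio of volumes and cannot be a serum concentration. The error is the same in Section 8.2 and the footnotes, so it is a unit error and not a conflict between them.

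**The case against.** The strongest reply has four parts.

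- **The protocol points to one place.** The synopsis and Section 8.1 refer to Section 8.2 for the regimen, and Tables 14 and 15 are schedules of assessments. This makes the matter less open than two rival texts with no link between them. It is still a cross-reference and not a rule of precedence, and the footnotes are themselves worded as dosing instructions.
- **Two of the conflicts are conditional.** Repeat rituximab needs a CD20 count that stays at or above 5%, and IVIG needs a low IgG. This stands: only children who meet a trigger are reached.
- **The prednisolone difference is small.** Assume a constant D from Day -7 to Week 12, about 7 + 84 = 91 days. The whole course is then 91 + 6.5625 = 97.56 D against 91 + 7.0 = 98 D, a difference of about 0.45%. The protocol already allows a twofold range in D, sirolimus adjustment to trough, and rescue steroids. This also stands.
- **Actual treatment is recorded.** Section 10.2 has added and stopped medications entered with dates, concomitant medication is reviewed at each visit from Visit B, and Section 14.2 says that no formal hypothesis is tested. Attribution of adverse events is therefore not shown to fail.

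These points limit the consequences. They do not remove the contradictions.

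**Conclusion.** The inconsistency is real on three points, and its demonstrated size is modest:

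- **Rituximab:** three permitted as-needed days against one, for children who meet the CD20 trigger.
- **Prednisolone:** a twofold difference for one week, 6.7% of the four-week taper. It is firm for infantile participants. The missing label in Table 14 footnote 16 may be a text-conversion fault, so that footnote needs checking before the same is said of juveniles.
- **IVIG:** a Day 1 label in the footnotes against Day 2 or later elsewhere, for children who meet the IgG trigger.

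The unit error is a separate correction. The prednisolone figures assume that each step lasts 7 days and that the footnotes are applied as written.

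Two stronger readings are tempting, and the documents support neither. A reader might infer that exposure is inconsistent across the planned maximum of 12 + 10 = 22 children and that this clouds the safety and expression results. But two conflicts are conditional, the third is firm only for the infantile group, and no effect on either kind of result is shown. A reader might also infer that some children would receive IVIG before the ICM/IT infusion. That follows only if the Day 1 label is taken literally. The same footnote requires the treatment infusion to be complete, Section 8.2 places IVIG after vector infusion, and the neighbouring CSF footnote calls Visit 1b Day -2, so day labels there are unreliable.

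**What to change.** Reconcile Section 8.2 with the grids and footnotes of Tables 14 and 15 so that one instruction applies on each of these points:

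- the days on which as-needed repeat rituximab is allowed, with the CD19/20 sampling row matched to them;
- the reference dose for the Week 15-16 prednisolone step in Section 8.2 and Table 15 footnote 17, with the wording of Table 14 footnote 16 checked against the source file;
- the first IVIG day in Table 14 footnote 19, Table 15 footnote 20, both grids and Section 8.2.

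Correct the unit of the IgG trigger wherever it appears. Add one sentence saying which text governs if Section 8.2 and the schedules differ. Which instruction is clinically right is for the sponsor and its clinicians to decide, and no view is offered here. The cost is a wording amendment with its usual review. It changes no endpoint, sample size or analysis; the only schedule row that might change is CD19/20 sampling.

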Twenty-three patients were enrolled in the study: 8 with infantile GM1 gangliosidosis, 15 with infantile GM2 gangliosidosis (9 with infantile TSD and 6 with infantile SD). The median age of onset of the first noted symptom for GM2 was 6 months and diagnosis at 15 months. The most common clinical changes in the infantile gangliosidoses were onset of hypotonia within the first 6 months of life, excessive oral and respiratory secretions, gastroesophageal reflux, dysphagia (followed by feeding-tube placement), and constipation. Utz and colleagues reported that most infantile GM2 patients had some motor developmental delay within the first 6 months of life and all patients had a delay by 12-months of age (Table 5).

Table 5: Motor Development Timeline

Infantile GM2 Motor Skills	N	Percent Never Gained	Patient Experienced	Age (Months) divided into 6-Month Intervals at which Motor Development Milestones Occurred				
				0 to 6	7 to 12	13 to 18	19 to 24	Experienced but age unknown
Gained independent head control	N=14	0%	100%	79%	7%			14%
Lost independent head control	N=14	-	93%		57%	21%	7%	7%
Gained ability to sit independently	N=13	62%	39%	31%	8%	15%		
Lost ability to sit independently	N=13	-	39%		23%			
Gained ability to crawl	N=13	100%	0%					
Lost ability to crawl	N=14	-	7%			7%		

Based on BSID-III data for GM2 patients only, adapted from Utz et al 2017.

Most patients had documented seizure disorders by 18 months of age, with the most common interval for seizure onset occurring between 13 to 18 months of age. Consistent with Bley et al. 2011, overall, motor skills that were gained within the first 6–12 months of life were lost in most GM2 patients by the age of 2 years. Most patients never gained the ability to crawl, and had a median survival for all patients with infantile-onset GM2 of 43.43 months (range for ages at death: 33.08–66.83 months).

[figure not shown]
There was no statistically significant difference between infantile-onset GM1 and GM2 patients when comparing the age of motor skills gained and motor skills lost. Gross motor skill scores (based on BSID-III Age Equivalent Scores for Gross Motor Domain) showed rapid decline in patients receiving two or more neurodevelopmental evaluations and reached the floor of the testing scale by 28 months of age for all tested patients (Figure 5).

Confidential Page 29 of 97

Clinical Study Protocol: AXO-GM2-001

Version 8.0, 09 June 2023

Figure 5: BSID-III Age-Equivalent Scores for Gross Motor Domain

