The ITI regimen will be stopped upon evidence of any of the following severe conditions for which no other cause has been identified: (1) intractable, severe opportunistic infections, not able to be managed with antibiotic, antifungal or antiviral therapy; (2) renal dysfunction (rising creatinine or BUN); (3) severe rash; (4) evidence of CNS problems including seizures or encephalopathy; (5) bleeding or clinically significant elevation of bleeding parameters.

Participants requiring discontinuation of the ITI regimen prior to Visit 1a (Day 1) will not be eligible for gene transfer and will be withdrawn from the study.

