8.2.1. Use of Rescue Steroids

Triggering criteria:

A modification of the corticosteroid regimen is indicated if the following events occur in the trial:

1. A positive gamma interferon ELISPOT response to AAVrh8 capsid or HEXA/B transgene peptide pools on two successive ELISPOT assays done on or prior to the 3-month post-dosing time point. Please note that if one ELISPOT is positive, the assay should be repeated within 1 to 2 weeks.

AND EITHER

2. A worsening of clinical neurological signs or symptoms felt to be indicative of inflammation and/or injury, including but not limited to physical and neurological examination, CSF analysis and neuroimaging studies.

OR

3. An increase in ALT to $2\times$ the pre-dosing level or $3\times$ the upper limit of normal.

If these conditions are met the following regimen will be completed:

- 1. Methylprednisolone administered IV at 10 mg/kg/day for 3 successive days.
- 2. Followed by resumption of prednisolone at 2 mg/kg/day for at least 3 weeks prior to resumption of the scheduled weaning protocol.
- 3. Adjustment of sirolimus dose to achieve a trough level of 10-15 ng/mL for at least 3 weeks prior to resumption of dosing to achieve a level of 7-12 ng/mL, followed then by the scheduled plans for continuation and weaning.

If these conditions are not met, but the indicators ALT and ELISPOT are trending higher, the PI may, at his or her discretion increase the prednisolone dose within the range of 1 to 2

Confidential Page 42 of 97

AXO-AAV-GM2

UMass Chan Medical School Clinical Study Protocol: AXO-GM2-001

Version 8.0, 09 June 2023

mg/kg/day and/or increase the sirolimus dose to achieve a trough level at a higher than the prior baseline, but still within the reference range (i.e., still less than 18 ng/ml).

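### Sections 8.2 and 8.2.1 can require one child's immunosuppression to be both stopped and intensified, with no stated precedence; separately, the two raised sirolimus limits in 8.2.1 need reconciling

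*Combined protocol and SAP*

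**What the plan says.** **Stop rule (protocol Section 8.2, end).** The text reads: "The ITI regimen will be stopped upon evidence of any of the following severe conditions for which no other cause has been identified". Five conditions follow. The fourth is "evidence of CNS problems including seizures or encephalopathy". If the regimen has to be discontinued before Day 1, the child is not dosed and leaves the study.

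**Rescue rule (Section 8.2.1).** The first element is always required: a positive response "on two successive ELISPOT assays done on or prior to the 3-month post-dosing time point". To this must be added one of two things:

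- "A worsening of clinical neurological signs or symptoms felt to be indicative of inflammation and/or injury"; or
- ALT at 2 times the pre-dosing level or 3 times the upper limit of normal.

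A single positive result is not enough: "if one ELISPOT is positive, the assay should be repeated within 1 to 2 weeks". Once the trigger is met, the regimen is mandatory: three days of IV methylprednisolone, then prednisolone at 2 mg/kg/day for at least 3 weeks, and "Adjustment of sirolimus dose to achieve a trough level of 10-15 ng/mL for at least 3 weeks" before a return to 7-12 ng/mL.

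**Discretionary increase (Section 8.2.1, end).** If the trigger is not met but ALT and ELISPOT are trending up, the investigator may raise prednisolone within 1-2 mg/kg/day and/or raise the sirolimus trough above its prior level, "but still within the reference range (i.e., still less than 18 ng/ml").

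**The concern.** The stop rule and the rescue rule act on the same drugs, prednisolone and sirolimus, in opposite directions. Both are written as instructions, not options. Neither refers to the other. The only thing that might separate them is the limit of the stop rule to conditions without another identified cause. The protocol does not say whether suspected immune inflammation, a positive ELISPOT, or a seizure expected from the disease is such a cause.

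This is first a child-safety matter. Two investigators who read the same text could take opposite actions on the same event. It also touches the evaluation. Section 8.2 gives protection of transduced cells as a purpose of ITI, and the Stage 2 primary endpoints are CSF HexA activity and BSID-III Gross Motor change in up to 10 children. Handling that depends on the reader would add variation. The documents give no basis for quantifying any effect on those endpoints.

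**Working it through.** No sample-size, power or alpha figure is involved, and Section 14.2 plans no formal test. The check is a comparison of the rules, plus subtraction for the sirolimus limits.

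**1. Write the rules as conditions.**

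- C: severe CNS problem (8.2)
- X: another cause has been identified (8.2)
- E: two successive positive ELISPOTs by 3 months (8.2.1)
- N: neurological worsening attributed to inflammation or injury (8.2.1)
- A: ALT rise (8.2.1)

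Stop = C and not X. Rescue = E and (N or A).

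**2. Count the overlap.** Five yes/no conditions give 2^5 = 32 patterns. Both rules hold when E and C are true, X is false, and at least one of N and A is true: 2 × 2 − 1 = 3 patterns.

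| E | N | A | C | X | Stop | Rescue |
|---|---|---|---|---|---|---|
| yes | no | yes | yes | no | required | required |
| yes | yes | no | yes | no | required | required |
| yes | yes | yes | yes | no | required | required |

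**3. Apply the reading most favorable to the plan.** Suppose that inflammation counts as another cause. Then N true makes X true, and the stop rule is off in the second and third rows. That leaves 3 − 2 = 1 pattern, the first row: two positive ELISPOTs, an ALT rise, and a severe CNS problem that remains unexplained. The rules still contradict each other there.

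**4. Timing.** Tables 14 and 15 schedule ELISPOT on Days 8, 15 and 22 and at Weeks 4, 6, 8, 10 and 12. Two orders of events are possible.

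- *Two positives come before the CNS event.* Both rules can be met at once.
- *The event comes after one positive.* During the 1 to 2 weeks to the repeat, E is not met, so rescue cannot apply and only the stop rule can. If the repeat is positive, the same child may then qualify for intensification. Neither section says whether a regimen already stopped under 8.2 is to be restarted under 8.2.1.

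The collision can arise only after dosing and depends on assays done by 3 months.

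**5. Sirolimus troughs (ng/mL).**

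| Situation | Trough | Nature |
|---|---|---|
| Routine | 7-12 | target |
| Rescue trigger met | 10-15, at least 3 weeks | required target |
| Trigger not met, ALT and ELISPOT trending up | below 18 | ceiling on discretion |

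The discretionary ceiling is up to 18 − 15 = 3 above the top of the rescue target and 18 − 12 = 6 above the routine top. Troughs from above 15 to just under 18 are therefore open only to a child who has not met the stated criteria for intensification.

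**The case against.** The strongest reply is that both rules are narrow. The stop rule needs a severe event with no other identified cause. Rescue needs two positive ELISPOTs as well as a clinical or ALT element, so neurological worsening alone triggers nothing. Another cause is naturally read as a cause other than ITI, and immune inflammation or the disease itself would then qualify. Section 4 names seizures as a primary symptom, and Section 13.10 tells investigators to weigh underlying illness and background frequency when judging adverse events.

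Much of this stands. It removes the conflict on the neurological route if that reading is adopted. But the reading is not written down, and it does not remove the ALT route. Four stronger inferences are tempting, and the documents do not support them:

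- *That any new neurological sign puts a child under opposite instructions.* The qualifiers above rule this out. While a repeat ELISPOT is pending, only one rule can apply.
- *That the conflict is an expected event.* Section 5 says "Most patients had documented seizure disorders by 18 months of age", with onset commonest at 13-18 months. Infants are dosed at 6-20 months, and exclusion 5 bars only drug-resistant seizures or status epilepticus. So seizures during ITI are plausible. This bears on the stop rule alone, and only if disease-related seizures are not another cause. The whole ITI period, Day -7 to Week 27, is likewise the stop rule's span, not the window of conflict.
- *That a seizure between Day -7 and Day 1 is part of the conflict.* Rescue cannot apply before dosing, and 8.2 states the consequence.
- *That the sirolimus limits are a further case of opposite instructions.* They cover mutually exclusive situations, and one is a target while the other is a ceiling. The discretionary path also adds no IV methylprednisolone, and the general Week 24-27 wean still applies to it.

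**Conclusion.** The point holds in this bounded form. Two mandatory rules can apply to one child and cannot both be followed, and the protocol gives no precedence. On the ALT route with an unexplained severe CNS problem this is so under either reading of the other-cause term. On the neurological route it is so only if suspected immune inflammation is not counted as another cause. The size is 3 of 32 logical patterns, or 1 of 32 under the favorable reading. The documents allow no estimate of how many children would be affected.

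The conclusion rests on reading both rules as binding, as they are worded, and on finding no precedence statement in the protocol. Documents that it refers to but that are not included, such as the DSMC Charter, could not be checked.

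The sirolimus ordering is a separate, smaller anomaly that needs an explanation. Because the main point is a contradiction between safety instructions and not merely missing detail, it must be corrected, rare or not.

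**What to change.** In the next amendment the sponsor must reconcile Sections 8.2 and 8.2.1:

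1. State which rule governs a child who meets both, before and after ELISPOT confirmation, and what follows if confirmation comes after a stop.
2. State whether suspected immune inflammation, and seizures expected from the disease, count as another cause.
3. Reconcile or explain the sirolimus figures for trigger met (10-15 ng/mL) and trigger not met (below 18 ng/mL).
4. Record in the eCRF which rule was applied at each ITI stop or intensification. Section 10.2 already captures start and end dates for medications added or discontinued; the rule applied is the missing item.

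Which rule or level is right is a clinical matter for the sponsor, and no view is taken here. The cost is a few sentences of protocol text and one eCRF field. A split of Week 48 results by ITI completion is not requested: with up to 10 participants it would condition on a post-treatment event and could be little more than a listing.
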